8.2. Informed consent and data privacy

Subjects included in this study will be identified among KPSC health plan members. Informed consent is not required because Boostrix is a licensed vaccine given to eligible KPSC members as part of routine clinical care. KPSC will obtain IRB approval for the use of patient data and to ensure protection of data privacy. Individual written Health Insurance Portability and Accountability Act (HIPAA) authorizations prior to initiating data collection will not be required.

8.3. Additional data

Additional summary level data will be provided from KPSC to GSK throughout the course of the study. This will include aggregated data from automated data sources, and will include the following:

- Monthly vaccine uptake report including uptake among pregnant women and non-pregnant individuals. Uptake among pregnant women will be broken down by women vaccinated at 27 weeks and above versus women vaccinated before 27 weeks.
- Quarterly cohort identification report, i.e., exposure data: This report will provide the uptake among pregnant women vaccinated on or after the 1st day of the 27th week of gestation, with additional inclusion/exclusion criteria applied as indicated in the study protocol.
- Quarterly identification of pre-specified adverse events and pregnancy outcomes.
- Quarterly report demonstrating the progress of chart review for the pre-specified adverse events (e.g. number of events identified, number in progress of being reviewed, number completed).

APPENDIX A AMENDMENTS AND ADMINISTRATIVE CHANGES TO THE PROTOCOL

GlaxoSmithKline Biologicals SA	
Vaccines R & D	
Protocol Amendment 2	
eTrack study number and Abbreviated Title	207221 (EPI-PERTUSSIS-047 VS US DB)
Amendment number:	Amendment 2
Amendment date:	Final: 12 November 2019
Rationale/background for changes:	
The protocol has been amended to modify the secondary endpoint of “post-partum hemorrhage (PPH)” to “transfusion during delivery hospitalization” as a proxy for severe PPH. We originally planned to identify PPH from automated diagnosis codes (ICD-9 and ICD-10) and then perform chart review to confirm the event. However, in October 2017 (ACOG Practice Bulletin PPH 2017), the threshold for estimated blood loss (EBL) for PPH diagnosis changed, affecting the comparison between the historical (~2012-2013) and the Boostrix exposed (2018-2019) cohorts. The potential for using EBL as an objective measure is limited by differential missingness of EBL data between these two cohorts as well as inconsistency in EBL measurements. We propose to use transfusion during delivery hospitalization as an indicator of severe blood loss and as a proxy for severe PPH. Transfusion can be captured by procedure codes, and transfusion data are stable across the study period. Transfusion is a relevant endpoint because hemorrhage that leads to blood transfusion is the leading cause of severe maternal morbidity in the United States (ACOG Practice Bulletin PPH 2017).

The following changes have been implemented.
 
 • Secondary objectives; Data collection Figure 1; Statistical methods Tables 6 and 7 - "Post-partum hemorrhage" was changed to "Transfusion during delivery hospitalization." • Case definitions; Data collection and management - Transfusion during delivery hospitalization is captured by procedure codes and will not be chart reviewed. • Data collection Figure 1; Statistical methods Table 7 - Transfusion will be identified among pregnant women with delivery hospitalizations. • Analysis of primary and secondary objectives; Statistical methods Table 7 - The statistical method for analyzing transfusion will be an adjusted Poisson 	

regression model. Robust variance estimation is not planned since the incidence is expected to be <2%.

Amended text has been included in ***bold italics*** and deleted text in ~~strikethrough~~ in the following sections:

Synopsis:

Secondary Objectives • ~~Post-partum hemorrhage~~ ***Transfusion during delivery hospitalization (as a proxy for severe post-partum hemorrhage)***

Endpoint(s) **Secondary**
• ~~Post-partum hemorrhage~~ ***Transfusion during delivery hospitalization***

With the exception of SGA, ~~and~~ preterm delivery, ***and transfusion***, medical records of the potential events will then be reviewed by trained research associates to confirm the diagnosis and to ascertain that it is an incident event.

Section 2.2 Secondary objectives

- ~~Post-partum hemorrhage~~ ***Transfusion during delivery hospitalization (as a proxy for severe post-partum hemorrhage)***

Section 4.2 Case definitions

With the exception of SGA, ~~and~~ preterm delivery, ***and transfusion***, chart review will be performed for the pre-specified maternal and infant adverse events to confirm the events and that the events are incident after the index date.

Section 5 Data collection and management

We will rely on automated data from the EHR to ascertain SGA, ~~and~~ preterm delivery, ***and transfusion***.

Figure 1. Illustration of data flow was updated and changes include:

- Post-partum hemorrhage secondary endpoint was changed to “Transfusion during delivery hospitalization”
- Modified sentence “All secondary endpoints ***but transfusion*** will be confirmed by medical record review”
- Secondary endpoints, footnote a, modified to say “Identified among pregnant women with ~~KPSC delivery~~ ***delivery hospitalization***”

Section 6.1 Primary and secondary pre-specified events of interest

Table 6 List of primary and secondary endpoints

Secondary endpoints	Post-partum hemorrhage Transfusion during delivery hospitalization
	Poor fetal growth
	Stillbirth/fetal death with or without congenital anomalies
	Neonatal death (within 28 days of birth)
	Maternal death (while pregnant or within 42 days of end of pregnancy)
	Placental abruption
	Preterm pre-labor rupture of membranes (PPROM)
	Congenital anomalies at birth and through 6 months of age
	Spontaneous abortion with or without congenital anomalies (only for women exposed to Boostrix before the 27 th week of gestation)
	Therapeutic abortion with or without congenital anomalies (only for women exposed to Boostrix before the 27 th week of gestation)

Section 6.2.2 Analysis of primary and secondary objectives

For events identified at delivery such as SGA, **and** preterm delivery, **and** ***transfusion during delivery hospitalization***, we will calculate crude incidence and 95% confidence intervals (CI) for each adverse event for the exposed and unexposed groups.

Table 7 Analytic population and statistical methods by endpoint

Secondary endpoints	Analytic population	Statistical Methods
Post-partum hemorrhage Transfusion during delivery hospitalization	Pregnant women with KPSC delivery hospitalization	Adjusted Poisson regression model, with robust variance estimate

## Publication Record

Version	Date	Primary Author	Description
Draft 1.0	14 June 2019	PPD	1 st Draft for GSK Review
Final 1.0	26 July 2019	PPD	Final version incorporating GSK comments/edits
Final 2.0	02 December 2019	PPD	Final version of the SAP amendment following the protocol amendment (signed 25NOV2019)

## **ABBREVIATIONS**

ACIP: Advisory Committee on Immunization Practices

ACOG: American College of Obstetricians

ADaM: Analysis Data Model

AE: Adverse Event

ASD: Absolute Standardized Difference

BMI: Body mass index

CA: Congenital anomalies

CDISC: Clinical Data Interchange Standards Consortium

CI: Confidence interval

DMP: Data Management Plan

ED: Emergency Department

EDD: Estimated Date of Delivery

EHR: Electronic Health Record

GSK: GlaxoSmithKline

HIV: Human immunodeficiency virus

ICD: International Classification of Diseases

KPSC: Kaiser Permanente Southern California

MRN: Medical Record Number

PHI: Protected Health Information

PPROM: Preterm pre-labor rupture of membranes

PPV: Positive Predictive Value

R&E: Research and Evaluation

RR: Relative Risk

SAP: Statistical Analysis Plan

SAS: Statistical Analysis System

SDTM: Study Data Tabulation Module

SGA: Small for Gestational Age

SOP: Standard Operating Procedures

Tdap: Tetanus, diphtheria, acellular pertussis

## 1. INTRODUCTION

Whooping cough, also referred to as pertussis, is a highly contagious respiratory disease primarily caused by the bacterium *Bordetella pertussis*. The disease is most severe in unvaccinated or incompletely vaccinated young infants. To increase the protection of newborns, in October 2012, the Advisory Committee on Immunization Practices (ACIP) recommended tetanus-diphtheria-acellular pertussis (Tdap) vaccine to be administered during pregnancy to all pregnant women, regardless of whether they have received Tdap previously. The optimal timing for Tdap administration is between 27 and 36 weeks of gestation.

Two Tdap vaccines (Adacel and Boostrix) were licensed for use in the United States in 2005. These vaccines were recommended for routine use in non-pregnant adolescents and adults when introduced. Both Adacel and Boostrix can be used interchangeably. There are limited post-marketing safety data on Boostrix during pregnancy. Through partnership between Kaiser Permanente Southern California (KPSC) and the sponsor, GlaxoSmithKline (GSK), we will conduct an observational, electronic health record (EHR) database study to assess the safety of Boostrix following routine immunization of pregnant women in a community setting.

This Statistical Analysis Plan (SAP) provides a detailed description of the data considerations, statistical methods, data analysis and results presentation as previously proposed in the protocol and Data Management Plan (DMP), where applicable. The SAP also describes quality assurance procedures and analytic data format standards.

## 2. STUDY OBJECTIVE

### 2.1. Primary objective

To rule out a two-fold increase (non-inferiority testing) in the incidence of each of the following maternal and infant adverse events (AEs):

- Preeclampsia and/or eclampsia
- Intra-uterine infections such as chorioamnionitis and endometritis
- Small for gestational age (SGA)
- Preterm delivery

among women who were vaccinated with Boostrix on or after the 1st day of the 27th week of gestation as compared to the incidence in a historical cohort of pregnant women (approximately January 1, 2012 to December 31, 2013) who were unvaccinated with any Tdap vaccine throughout their pregnancy.

The null hypothesis and alternative hypothesis for test of relative risk (RR) are:

$$H_0: RR \geq 2$$

$$H_a: RR < 2$$

### 2.2. Secondary objective

1. To explore differences (superiority testing) in the incidence rate of other maternal and infant AEs, namely:
  - Transfusion during delivery hospitalization
  - Poor fetal growth
  - Stillbirth/fetal death with or without congenital anomalies
  - Neonatal death (within 28 days of birth)
  - Maternal death (while pregnant or within 42 days of end of pregnancy)
  - Placental abruption
  - Preterm pre-labor rupture of membranes (PPROM)
  - Congenital anomalies (CA) at birth and through 6 months of age

between women who were vaccinated with Boostrix on or after the 1st day of the 27th week of gestation and a historical cohort of pregnant women (approximately January 1, 2012 to December 31, 2013) who were unvaccinated with any Tdap vaccine throughout their pregnancy.

The null hypothesis and alternative hypothesis for test of RR are:

$$H_0: RR = 1$$

$$H_a: RR \neq 1$$

2. To describe the incidence of maternal and infant AEs described above, as well as the incidence of spontaneous and therapeutic abortion with or without congenital anomalies, in pregnant women who were vaccinated with Boostrix before the 27th week of gestation.

### **3. STUDY DESIGN**

#### **3.1 Overview of study design**

This is an observational retrospective matched cohort study. The study will be conducted among pregnant women who are members of KPSC.

The exposed cohort (from the 27th week of gestation) will consist of pregnant women who received the Tdap vaccine (Boostrix) on or after the 1st day of the 27th week of pregnancy during the vaccination period at ob-gyn clinics of seven selected medical centers. Approximately 15,000 women vaccinated with Boostrix will be included in this study over approximately a one-year period from January 2018 to January 2019.

The unexposed cohort will consist of women, pregnant sometime during the approximate estimated period from 1/1/2012 to 12/31/2013 who never received Tdap vaccine during pregnancy. The unexposed cohort of pregnant women will be matched 1:1 to the exposed cohort of pregnant women for comparisons of maternal and infant AEs between the two cohorts.

Subject-level data will be collected for pregnant women and their infants through the EHR. For each individual pregnant woman, analytical follow up will begin on the date they receive the Boostrix vaccine, or the index date for the unvaccinated cohort, and will end on the date of

disenrollment or the end of pregnancy, whichever came first. For the maternal death endpoint, pregnant women will be followed for 42 days after the end of pregnancy. Infants born in KPSC hospitals will be followed for 6 months.

In addition, women vaccinated with Boostrix before the 27th week of gestation, with membership at the date of vaccination, and who were not vaccinated with any other Tdap vaccine at any other time during the pregnancy will be included for a descriptive analysis (single arm).

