There were 19,554 (98.7%) pregnant women who received Tdap vaccination at or after 27 weeks of pregnancy (Table 4). There were 18,611 (94.0%) women who were vaccinated between 27 and 36 weeks gestation.

Table 4 Gestational age of women at Tdap vaccination during pregnancy at seven selected medical centers at Kaiser Permanente Southern California, 2016

Gestational age at vaccination	Frequency	Percent
<27 weeks	250	1.3%
27 weeks to 32 weeks	15,111	76.3%
33 weeks to 36 weeks	3,500	17.7%
>36 weeks	943	4.8%
TOTAL	19,804	100%

Note: Only those women meeting eligibility criteria, including membership, will be included in the analysis.

Rationale for historical comparison cohort

The estimated period of 1/1/2012-12/31/2013 was chosen for the unvaccinated comparison group because Tdap uptake ranged between 27% and 38% during this time (Table 5). The aim is to restrict the unvaccinated population to approximately 2012-2013 to minimize the concerns of confounding by indication. Given that Tdap uptake exceeded 65% starting in 2014, a concurrent unvaccinated cohort will yield a small and selective sample, and is not representative of an unvaccinated group.

Table 5 Tdap vaccine receipt during pregnancy at Kaiser Permanente Southern California, 2011-2016

Year	Tdap during pregnancy		No Tdap during pregnancy	
	Frequency	Percent	Frequency	Percent
2011	18325	40.0%	27471	60.0%
2012	13128	27.6%	34486	72.4%
2013	18309	38.3%	29519	61.7%
2014	32660	65.3%	17366	34.7%
2015	35754	68.4%	16513	31.6%
2016	38475	69.3%	17058	30.7%

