### **3.2 Study population, exposures, outcomes and covariates**

#### **3.2.1 Study populations/subgroups**

##### *Study population for main analysis (primary objective and secondary objective #1)*

- Pregnant women received prenatal care at KPSC
- Exposed cohort: vaccinated with Boostrix on the 1st day of the 27th week of pregnancy or later during the pregnancy and were not vaccinated with any other Tdap vaccine at any other time during the pregnancy or
- Unexposed cohort: pregnant at least one day during the approximate estimated period between 1/1/2012-12/31/2013 and did not receive any Tdap vaccine during the pregnancy
- Continuous membership (allowing up to a 31-day gap) between the 1st day of the 27th week of pregnancy and the index (vaccination) date

The unexposed cohort will be 1:1 matched to the exposed cohort on age at pregnancy start ( $\pm 1$  year), race/ethnicity (White, Black, Hispanic, Asian, and Other), and multiple gestation (yes/no). Every unexposed woman will be assigned an index date that is determined by the number of days from pregnancy start to the Boostrix vaccination date of her matched exposed woman. The same number of days calculated in the exposed woman will be added to the pregnancy start of the unexposed woman to determine her index date.

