##### *Subgroups for endpoint-specific analysis*

For some maternal and infant AEs (endpoints), additional restriction criteria will be applied. We will exclude individuals who do not meet the restriction criteria, but not the matched pair. Analysis will be conducted on a subgroup of the population:

- Small for gestational age (SGA): Infants 1) live born, 2) singleton, and 3) born in KPSC hospitals. Rationale: The evaluation of SGA is limited to singleton births because the reference values for SGA definition are established based on singleton births. The birth weight of infants born outside KPSC hospitals is not captured in claims, and such infants are therefore excluded for this endpoint.

- Preterm delivery: Pregnant women 1) with live birth and 2) with index (vaccination) date prior to 37 weeks gestation. Rationale: Pregnant women with an index (vaccination) date on or after 37th week of gestation are not at risk of preterm delivery, and are therefore excluded for this endpoint.
- Preterm pre-labor rupture of membranes (PPROM): Pregnant women with index (vaccination) date prior to 37 weeks gestation. Rationale: Pregnant women with an index (vaccination) date on or after 37th week of gestation are not at risk of PPROM, and are therefore excluded for this endpoint.
- Transfusion during delivery hospitalization: Pregnant women with delivery hospitalization. Rationale: Transfusion can be captured by procedure codes during the delivery hospitalization.
- Stillbirth/fetal death: Pregnant women with pregnancy outcome. Rationale: Pregnant women with unknown pregnancy outcome are considered as missing data, and are therefore excluded for this endpoint.
- Neonatal death (within 28 days of birth) and congenital anomalies at birth and through 6 months of age: Infants 1) live born and 2) born in KPSC hospitals. Rationale: Infants born outside KPSC hospitals may not be captured and may not be able to be linked back to their pregnant mothers, and are therefore excluded for this endpoint.

Analysis for preeclampsia and/or eclampsia, intra-uterine infections, poor fetal growth, placental abruption, and maternal death will be conducted on all pregnant women eligible for the main analysis and descriptive analysis.

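### Unexposed women are selected on staying Tdap-free until delivery, which on its own lowers the preterm-delivery RR by a few per cent and is anti-conservative close to the margin of 2

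*SAP*

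**What the plan says.** SAP 3.1 describes the unexposed cohort as women pregnant in about 2012-2013 "who never received Tdap vaccine during pregnancy". The eligibility list in SAP 3.2.1 repeats the condition: "did not receive any Tdap vaccine during the pregnancy". The primary objective (protocol 2.1, SAP 2.1) also uses a comparator unvaccinated for the whole pregnancy.

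Follow-up starts later than pregnancy start: "analytical follow up will begin on the date they receive the Boostrix vaccine, or the index date for the unvaccinated cohort". A control's starting day is assigned in SAP 3.2.1 as follows: "The same number of days calculated in the exposed woman will be added to the pregnancy start of the unexposed woman to determine her index".

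Tdap was in use in the comparator years. Protocol 3.2 states that "Tdap uptake ranged between 27% and 38% during this time", and its Table 5 gives 27.6% for 2012 and 38.3% for 2013. Protocol 4.1 allows further years to be added if needed.

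Preterm delivery is a primary endpoint. It is analysed as a proportion among women with a live birth and an index date before 37 weeks (SAP 3.2.1, 4.2). Non-inferiority is concluded if the upper 98.75% limit for the adjusted RR is below 2. SAP 5.4 discusses secular confounding and confounding by indication only.

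**The concern.** A control who is Tdap-free on her index day and vaccinated three weeks later is removed. A control who delivers before she could be vaccinated is kept. Eligibility thus depends on the interval between index and delivery, and the length of that interval is what the preterm endpoint measures. Matching on the index day aligns the start of follow-up but does not undo selection on later events. Excluding index dates from 37 weeks onward does not undo it either.

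In a superiority test for harm, a raised control rate would hide a signal. In this non-inferiority test it makes a two-fold increase easier to rule out. The plan's one quantified allowance for design bias, the RR of 1.25 in SAP 3.3, is for bias in the opposite direction. Signal investigation (SAP 4.5) starts only when a two-fold risk is not ruled out, so a result that is too favourable would prompt no further work.

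**Working it through.** **1. The plan's own figure.** Inputs from SAP 3.3: n = 15,000 per cohort, control risk p2 = 0.01, p1 = 1.25 × 0.01 = 0.0125, margin R = 2, one-sided alpha 0.025/4 = 0.00625 (z = 2.498). The restricted estimate of the control risk under p1 = 2·p2 is q = [3.0325 − √(3.0325² − 4·4·0.0225)]/8 = 0.00749, with 2q = 0.01499.
- SE under the null: √{[0.01499·0.98501 + 4·0.00749·0.99251]/15,000} = 0.001723.
- SE under the alternative: √{[0.0125·0.9875 + 4·0.01·0.99]/15,000} = 0.001861.
- Power = Φ[(0.02 − 0.0125 − 2.498·0.001723)/0.001861] = Φ(1.72) = 95.7%, as stated.

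The power figure is correct. The issue is bias, which that calculation does not address.

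**2. The selection as a formula.** Take women still pregnant and Tdap-free on the index day, with preterm risk p. Let v1 and v0 be the probabilities of Tdap between index and delivery for those who deliver preterm and at term. Among women who remain never vaccinated, preterm risk is multiplied by

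k = (1 − v1) / [1 − p·v1 − (1 − p)·v0].

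Preterm deliverers have less time to be vaccinated, so v1 < v0 and k > 1. The RR is divided by k. If controls are defined as Tdap-free at index, the condition on v1 and v0 disappears. With no vaccine effect and vaccination timing independent of delivery timing, the RR is then 1.00. As an extreme, suppose all uptake u falls after index and none among preterm deliverers: k is then at most 1/(1 − u), or 1/(1 − 0.276) = 1.38 to 1/(1 − 0.383) = 1.62.

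**3. Inputs for a realistic size.**
- Uptake (protocol Table 5): 27.6% and 38.3%; pooled (13,128 + 18,309)/95,442 = 32.9%.
- Index timing (protocol Table 4, 2016): 1.3% before 27 weeks, 76.3% at 27-32, 17.7% at 33-36, 4.8% after 36.
- Women with an index date before 37 weeks: 1 − 943/19,554 = 95.2% of 15,000, about 14,280 per cohort.
- Assumed, because the documents do not give them: preterm risk, gestational age at delivery, and when in pregnancy women were vaccinated in 2012-13.

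**4. Results when the true RR is 1** (uptake 27.6-38.3%):

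| Assumed 2012-13 vaccination timing | Assumed preterm risk | RR estimated |
|---|---|---|
| As in Table 4 (k = 1.04-1.07) | 6-10% (5-10% gives the same) | 0.93-0.96 |
| Spread over 20-38 weeks | 6-10% | 0.92-0.95 |
| Spread over the whole pregnancy | 6-10% | 0.94-0.97 |
| Half before 27 weeks (k = 1.03-1.05) | 5-10% | 0.95-0.97 |

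Across plausible timings the range is about 0.92-0.98. Controls Tdap-free at index give 1.00 throughout.

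**5. Effect on the test.** The pass probability is Φ[ln(2/RR_obs)/SE − 2.498], with SE = √[(1 − p1)/(n·p1) + (1 − p2)/(n·p2)].

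One case in full: half of vaccinations before 27 weeks, uptake 38.3%, overall preterm risk 8%. Preterm risk after index is 0.0702 among women Tdap-free at index and 0.0734 among the never vaccinated, so k = 0.0734/0.0702 = 1.046. A true RR of 2 appears as 2/1.046 = 1.912. With p1 = 0.1404 and n = 14,280, SE = 0.0362, and the pass probability is Φ(0.0450/0.0362 − 2.498) = Φ(−1.26) = 10.4%. The nominal value is 0.6%.

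- Table 4 timing: a true RR of 2 appears as 2/1.07 = 1.87 to 2/1.04 = 1.92 and passes with probability 5.5-33%.
- With the RR multiplied by 0.92-0.95, the pass probability is 12-64% at a true RR of 2.0, 1-10% at 2.1 and below 0.3% at 2.2.
- At a true RR of 1.0-1.5 it is about 1 with or without the selection.

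**6. If later years were added.** At 65.3% uptake (2014) and Table 4 timing, an RR of 1 would be estimated as about 0.81-0.83 and a true RR of 2 as about 1.6-1.65.

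**The case against.** **The conclusion is unlikely to change.** This stands. The study passes at a true RR near 1 and fails at 2.2 whether or not the selection is present. A reader might infer that the plan is heading for a false non-inferiority result. The figures do not support that, because only a narrow band around 2 is affected.

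**The margin already allows for bias.** This stands in part. SAP 5.3 says the possible size of bias was considered in choosing 2, but it gives no figure.

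**The net direction is unknown.** This stands. The calculation isolates one mechanism, and SAP 5.4 lists secular changes that could move the RR either way. A reader might infer that the reported preterm RR will be too low overall. The documents do not establish that.

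**Larger figures are possible.** If 2012-13 vaccination were spread over 27-39 weeks, the RR would be 0.84-0.89. That fits the history poorly. Earlier guidance was any stage or from 20 weeks (protocol 1.1), and the 27-36 week guidance reached this health system only in December 2012 (protocol 3.1). Vaccination before the index day cannot cause this selection. Adding years after 2013, when uptake rose ("Given that Tdap uptake exceeded 65% starting in 2014"), also looks unlikely to be needed. Table 5 shows 34,486 + 29,519 = 64,005 pregnancies without Tdap in 2012-13, against about 15,000 controls required.

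**The exposed definition also looks forward.** Correct: exposed women must have no other Tdap at any other time in the pregnancy (SAP 3.2.1). It would be wrong to say that they are classified only on events up to index. That rule removes only women with a second dose in the same pregnancy, so it should matter far less.

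**Redefining controls brings its own problem.** This stands if later vaccinees are simply kept. In a simulation with a doubled preterm hazard after vaccination, a true RR of 1.91-1.95 was estimated as 1.63-1.73 with later vaccinees kept, against 1.79-1.87 under the plan. The repair therefore needs censoring at later Tdap.

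**Conclusion.** The point holds for preterm delivery as a modest bias whose direction is known. Taken alone, selecting controls on staying Tdap-free to delivery raises the control preterm rate and lowers the RR. The estimate at a true RR of 1 is about 0.93-0.96 with Table 4 timing and about 0.92-0.98 across other plausible timings. It weakens error control close to the margin of 2, and would do so more if years with over 65% uptake were added. It does not alter the conclusion for a true RR near 1 and says nothing about the net bias of the historical comparison.

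The size rests on assumed preterm risk, gestational age at delivery and 2012-13 vaccination timing, and on vaccination timing being independent of delivery timing. For PPROM the same selection can be expected, but it was not calculated. That endpoint is tested for superiority on person-time, so the non-inferiority argument does not carry over.

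**What to change.** Keep the primary analysis and its never-vaccinated comparator. Make three additions to the SAP.

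1. **One pre-specified sensitivity analysis, preterm delivery only.** Draw matched controls who are still pregnant and Tdap-free on the index day. Analyse time to delivery on the gestational-age scale, entering at index and censoring at later Tdap receipt, disenrollment or 37 weeks 0 days. State how a non-live birth before 37 weeks is handled, since the endpoint is defined among live births.
2. **The uncensored version beside it**, keeping later vaccinees as unexposed. Note that contamination pulls this version toward 1 if the vaccine has an effect.
3. **A sentence in SAP 5.4** naming the selection and its direction for preterm delivery. For PPROM, state the limitation only: PPROM is chart-reviewed, so a new control set would need further abstraction.

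The cost is a second control draw and one extra time-to-event model, because preterm delivery is currently analysed as a simple proportion. No chart review is needed to ascertain preterm delivery, which comes from automated data (protocol 5, SAP 3.2.3).
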